6.2.2 Secondary efficacy endpoint

The same estimand as the primary efficacy estimand - except the endpoint - will be used for the secondary efficacy endpoints analyses. The IEs a), b) and c) will be handled as described in section 6.2.1.

For the identification of at least 1 superior effective dose of BAY 1817080 compared to placebo in terms of the absolute change in mean worst EAPP from baseline to end of intervention, estimates and CIs will be derived from MMRM. The mean worst EAPP at baseline, the region (Japan vs. ROW excluding China) visit and treatment*visits are set as covariates.

Summaries will be provided by treatment group and overall. Analyses will be performed including the Elagolix population arm.

6.2.3 Other endpoints

The descriptive analyses of the other endpoints described in the following subsections will be based on the FAS and presented by treatment group.

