4.1 Overall Design

- **Study design summary:** Multicenter, randomized, placebo- and active comparator controlled, double blind to placebo and open-label comparator; parallel group
- Intervention group: Parallel
- **Study duration:** Maximum of 233 days (Follow-up 1: subjects with 38±3 days follow-up) or 285 days (Follow-up 2: subjects with 90±3 days follow-up)
- Intervention duration: 84 days (+3 days)

27 JAN 2022 Page: 30 of 99

• Study Periods:

- o Screening
- o Pre-intervention
- o Intervention
- o Follow-up
- **Diagnosis group:** Endometriosis

Approximately 840 participants will be screened to start study intervention in about 420 randomized participants for at least 50 participants evaluable for the primary analysis (i.e. included in the pPPS) per intervention group. The primary analysis will not include the participants enrolled based on visually-confirmed diagnosis, i.e. about half of the women randomized in Japan, nor the participants randomized in China, who are mainly included to generate further data using the ESD in this population. Refer to Section 9.3 for further information of inclusion of participants into analysis sets.

Screening period

The duration of the screening period should be kept to a minimum. Investigators are advised to schedule screening visit during the 2nd half of the menstrual cycle, ideally closely before the next menstrual bleeding, to minimize the time in the screening period. In rare cases of technical issues it may not be feasible to complete the screening within 70 days. In these cases the screening period may be extended over 70 days with prior approval from Sponsor, on case by case basis.

Daily ESD completion will begin from Visit 1a. The 28-day assessment period for ESD eligibility criteria (see Section 5.1) starts from Day 1 of the first menstrual bleeding on or after Visit 1a (Day 1 of the menstrual cycle is defined as the first of the 2 consecutive days with more than spotting).

Randomization

Participants who fulfill all eligibility criteria will be randomized at Visit 1b in a ratio of 1:1:1:1:1 into one of the 5 treatment groups:

- Treatment group 1: 150 mg of BAY 1817080 BID
- Treatment group 2: 75 mg of BAY 1817080 BID
- Treatment group 3: 25 mg of BAY 1817080 BID
- Treatment group 4: placebo
- Treatment group 5: elagolix 150mg QD

Participants from Japan and China will be randomized to treatment groups 1 through 4.

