5.1 Inclusion Criteria

Participants are eligible only if all of the following criteria apply:

Age

1. Participant must be \geq 18 years of age at the time of signing the informed consent

Type of Participant and Disease Characteristics

- 2. Visually-confirmed endometriosis: detection of endometriotic lesions during laparoscopy or laparotomy (with or without pathological diagnosis) within 10 years but no less than 8 weeks from Visit 1a (surgically diagnosed endometriosis).
 For Japan only and limited to no more than half of all randomized Japanese participants: the diagnosis can be based on previous imaging (i.e. endometriosis lesion detected by ultrasound or MRI). If the participant was diagnosed by ultrasound, the lesion must be visualized again by ultrasound at the screening visit. If the participant was diagnosed by MRI, the diagnosis must have been made within 12 months before Visit 1a (clinically diagnosed endometriosis).
- 3. Both sub-criteria regarding pain symptoms must be fulfilled:
 - At Visit 1a, participant presents self-reported moderate to severe pain which based on the judgement of the investigator carries a reasonable likelihood to translate into a severity of pain symptoms sufficient to fulfil the eligibility criterion and be caused by endometriosis, and
 - During the screening period at least 24 daily ESD entries during the 28 consecutive days starting on the first day with menstrual bleeding at or after Visit 1a and entries in the ESD item 1a ('worst pain' on the daily numerical rating scale) sum up to 98 or more.

27 JAN 2022 Page: 37 of 99

- 4. Willingness to use standardized rescue pain medications for EAPP (i.e. ibuprofen, acetaminophen and tramadol) and not use any prophylactic pain medication, according to investigator's instruction
- 5. Ability to swallow the study intervention, i.e., the different kinds of tablets, as complete units
- 6. Good general health (except for findings related to endometriosis) as proven by medical history, physical and gynecological examinations and laboratory test results
- 7. Normal or clinically insignificant cervical cytology not requiring further follow-up:
 - A cervical cytology sample has to be obtained during screening, or
 - A documented normal result has to be available from cervical cytology conducted within 12 months prior to Visit 1a.

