9.2 Sample Size Determination

Approximately 840 participants will be screened to start study intervention in about 420 randomized participants for at least 50 participants evaluable for the primary analysis (i.e. included in the pPPS) per intervention group. The primary analysis will not include the participants enrolled based on visually-confirmed diagnosis, i.e. about half of the women randomized in Japan, nor all the participants randomized in China, who are mainly included to generate further data using the ESD in this population. Refer to Section 9.3 for further information of inclusion of participants into analysis sets.

If blinded data reviews indicate an unexpected high number of screening failures due to the COVID-19 pandemic, enrollment may be increased.

27 JAN 2022 Page: 66 of 99

Sample size calculations were performed for establishing evidence of a drug effect across the doses, that is, detecting a statistically significant dose response signal for the primary efficacy outcome in this study using the MCP-Mod approach. They are based on the following assumptions:

- change in mean EAPP under placebo after 12 weeks of -2.3
- maximum change in mean EAPP of -1.2 for BAY 1817080 over placebo
- standard deviation of 2.5 for all dose groups
- a set of plausible dose-response shapes including Emax and sigmoidal Emax models (chosen based on literature review and historic in-house data)
- random allocation of participants to dose groups according to a 1:1:1:1 ratio,

A sample size of 50 participants per dose groups will have appr. 90% power (averaged across the set of dose-response shapes) to demonstrate a dose- response relationship, using a one-sided test at a type I error rate of α =0.10.

Approximately 70 participants for primary analysis will be randomized to each treatment group to achieve 50 evaluable participants for each treatment group.

In addition, 28 participants from Japan with clinical diagnosis, as well as 28 participants from China will be randomized 1:1:1:1, but will not be included in the primary analysis.

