Although not formally included in the sample size determination, the exploratory elagolix 150mg treatment group is planned to be of about the same size as the other treatment groups. As participants from Japan and China cannot be randomized to the elagolix 150mg arm, the randomization ratio outside of Japan and China will be 3:3:3:3:4 (Placebo:25 mg:75 mg:150 mg:elagolix). This will provide similar sizes of all treatment groups overall.

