Endometriosis is a hormone-dependent gynecological disease characterized by painful symptoms like dysmenorrhea, chronic and non-cyclic pelvic pain, and dyspareunia. Considering all available treatment modalities, recent data confirm a significant degree of unmet medical need, since up to 70 % of treated patients have persistent symptoms like chronic pelvic pain that are not sufficiently managed (Bayer market research, 2009; 21,700 women in 8 countries).

Pathologically the disease is defined by the presence of endometrial tissue outside the uterine cavity (endometriotic lesions). The endometrial lesions exhibit signs of inflammation. BAY 1817080 demonstrated robust efficacy in different *in vivo* and *in vitro* models including effects on neurogenic inflammation with high relevance for endometriosis. BAY 1817080 is an antagonist for the P2X3 receptor that is an important mediator of nociception and other disorders with an over-activation of sensory nerve fibers and can be found in nerve fibers of endometriotic lesions. Thus, BAY 1817080 is believed to carry the potential to relieve endometriosis-associated pelvic pain and improve quality of life of women with endometriosis.

This Statistical Analysis Plan (SAP) is based on:

- the clinical study protocol BAY 1817080 / 20584, version 3.0, amendment number 2 dated 27 JAN 2022.

2. Study Objectives

The objective of this study was to identify the optimal dose of P2X3 receptor antagonist BAY 1817080 in women with symptomatic endometriosis and further assess efficacy and characterize safety and tolerability profile of BAY 1817080.

The **primary** study objective was to

- assess the dose-response relationship and demonstrate efficacy of BAY 1817080 compared to placebo in women with symptomatic endometriosis

The **secondary** study objectives were to

- identify at least 1 superior effective dose of BAY 1817080 compared to placebo
- evaluate the safety and tolerability of 3 doses of BAY 1817080 compared to placebo and elagolix 150mg in women with symptomatic endometriosis

Other objectives were to

- assess efficacy of BAY 1817080 compared to placebo and elagolix 150mg in the treatment of EAPP at weeks 4 / 8 and end of intervention period
- assess efficacy of BAY 1817080 compared to placebo and elagolix 150mg in the treatment of EAPP during days with vaginal bleeding (dysmenorrhea/menstrual pelvic pain) at weeks 4/ 8 and end of intervention period

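### Elagolix could be allocated only outside Japan and China, but the SAP's by-arm tables set it beside blinded arms pooled over all regions

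*SAP*

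**What the plan says.** **Allocation.** Protocol 4.1 states: "Participants from Japan and China will be randomized to treatment groups 1 through 4". These are the three BAY 1817080 doses and placebo. Protocol 9.2 adds that "the randomization ratio outside of Japan and China will be 3:3:3:3:4", with elagolix as the 4. Region and type of diagnosis are the two stratification factors (Protocol 4.1).

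**Objectives.** SAP 2 keeps elagolix as a comparator after the revision for early termination. A secondary objective is to "evaluate the safety and tolerability of 3 doses of BAY 1817080 compared to placebo and elagolix 150mg". Among the other objectives is to "assess efficacy of BAY 1817080 compared to placebo and elagolix 150mg in the treatment of EAPP during days with vaginal bleeding", with parallel objectives for overall EAPP and for non-bleeding days.

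**Analyses.** The other endpoints in SAP 6.2.3 "will be based on the FAS and presented by treatment group". SAP 6.4 is descriptive on the SAF, with AE tables by intervention group. SAP 6.4.1.1 adds a logistic regression for taste-related AEs that gives odds ratios and p-values, with treatment as the only named factor. It does not say whether elagolix is one of the treatments. In SAP 5.1 neither the FAS nor the SAF has a regional restriction; the protocol's FAS (Table 9–1) leaves out China but keeps Japan. Region is a covariate only in the MMRMs of SAP 6.2.1.1 and 6.2.2, both on the pPPS.

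**The concern.** Randomisation supports a comparison with elagolix only among women who could have received it. In the pooled tables the elagolix column comes from one region, while each blinded column also holds women from Japan and China, some of them with an imaging-based diagnosis. A regional difference in outcome or in reporting habits then enters the contrast as if it were a treatment difference. The same applies to any elagolix odds ratio from the taste-AE model.

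The exposed comparisons with elagolix are bleeding-day and non-bleeding-day EAPP, the other PROs, the FAS-based EAPP tables, and safety. For the secondary safety objective these tables are the planned evidence. SAP 7 records that subgroup and sensitivity analyses were removed, so no by-region output remains as a check.

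**Working it through.** **Inputs**
- About 420 randomised (Protocol 9.2).
- "28 participants from Japan with clinical diagnosis, as well as 28 participants from China will be randomized 1:1:1:1" (Protocol 9.2).
- "Approximately 70 participants for primary analysis will be randomized to each treatment group" (Protocol 9.2).
- Imaging-based diagnosis in Japan is "limited to no more than half of all randomized Japanese participants" (Protocol 5.1).
- SD 2.5 and maximum effect 1.2 for overall mean EAPP (Protocol 9.2).
- Taste-related AE rates of 20.5% at the highest dose and 5.1% at the lowest in study 18184 (Protocol 2.3.1).

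**1. Reproducing the planned arm sizes.** Let J be the number randomised in Japan. The rest of the world then has 420 − 28 − J = 392 − J women. Each blinded arm takes 3/16 of these and elagolix takes 4/16. Women eligible for the primary analysis, per blinded arm:

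3/16 × (392 − J) + (J − 28)/4 = 66.5 + 0.0625 J

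Setting this to 70 gives J = 56, and 28/56 is exactly the cap of one half. Then:
- rest of the world: 336, giving 63 per blinded arm and 84 on elagolix;
- Japan and China: (56 + 28)/4 = 21 per blinded arm;
- blinded arm total: 63 + 21 = 84, so all five arms have 84, and 5 × 84 = 420.

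This matches the plan's 420, its 70 per arm and its aim of similar arm sizes. Protocol 4.1 also mentions 1:1:1:1:1 for the five groups; the calculation uses the ratios of Protocol 9.2 and SAP 3, which reproduce equal arms.

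**2. Regional and diagnostic mix**

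| Share of arm | Each blinded arm | Elagolix |
|---|---|---|
| Japan or China, SAP FAS | 21/84 = 25% | 0/84 |
| Japan, protocol FAS (no China) | 14/77 = 18% | 0/84 |
| Clinical diagnosis, SAP FAS | 7/84 = 8% | 0/84 |

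If 70 is a rounded value, J can rise to 64, where 66.5 + 0.0625 × 64 = 70.5. The shares are then 23/84.5 = 27% and 16/77.5 = 21%. J below 56 would breach the cap.

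**3. Effect on a mean difference.** With share s from Japan and China, and D the regional difference in mean outcome within the blinded arm, the pooled arm mean is the rest-of-world mean plus s × D. The contrast with elagolix is off by s × D. D is not in the documents. Over an assumed range of 0 to 1 NRS point:
- SAP FAS: 0.25 × D = 0 to 0.25 points; protocol FAS: 0.18 × D = 0 to 0.18 points.
- The upper end, 0.25/1.2, is 21% of the maximum effect assumed for BAY 1817080 over placebo.
- SE at 84 per arm: 2.5 × √(1/84 + 1/84) = 0.386, so up to 0.25/0.386 = 0.65 SE.
- At the plan's evaluable rate, 84 × 50/70 = 60 per arm: SE 0.456, so up to 0.25/0.456 = 0.55 SE.

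For AE percentages, each 10 percentage points of regional difference gives 0.25 × 10 = 2.5 percentage points.

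**4. Taste-AE model, if elagolix is included.** Assume a 20.5% rate in the BAY arm outside Japan and China, and k times that rate in Japan and China. The pooled rate is 0.205 × (0.75 + 0.25 k).

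| k | Pooled rate | Multiplier on the BAY versus elagolix odds ratio |
|---|---|---|
| 0.5 | 0.179 | 0.85 |
| 1 | 0.205 | 1.00 |
| 2 | 0.256 | 1.34 |

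Starting from 5.1% instead, k = 0.5 and k = 2 give about 0.87 and 1.27.

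**The case against.** Elagolix is called exploratory, lies outside the sample size calculation, and appears in these sections mainly in descriptive columns; no formal elagolix contrast is specified in SAP 6.2.3. The modelled efficacy comparison, in SAP 6.2.2, includes elagolix, adjusts for region and runs on the pPPS, which leaves out China and clinically diagnosed women. It can also supply weeks 4 and 8. The taste-AE model is meant to assess dose-dependency, which reads most naturally as placebo and the BAY doses, and these are balanced by region. The assumed 1 NRS point is large beside an effect of 1.2, and SD 2.5 is stated only for overall EAPP, so the SE figures do not describe bleeding-day EAPP or the other PROs. Race, ethnicity and counts by investigator and arm (SAP 6.1.1 and 6.1.2) would let a careful reader see the imbalance. Restriction also leaves open-label elagolix with patient-reported outcomes (Protocol 4.2) and the absence of the extra liver visits in that arm (Protocol 1.3).

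Most of this stands as a limit on importance. It does not remove the problem. A descriptive column is still not comparable when its population differs by design, and comparison with elagolix is a stated objective. Race and site counts hint at the imbalance without correcting it. The taste-AE point remains conditional, because the SAP does not say which treatments enter the model.

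**Conclusion.** The concern holds, as a matter worth considering rather than a threat to the trial's main result. By design, about 25% of each blinded arm (18% under the protocol FAS) comes from regions where elagolix could not be allocated, against 0% of the elagolix arm, and the pooled tables neither restrict nor adjust for this. The allocation facts are firm. The shares are planned figures that rest on the stated 420, 28, 28 and 70; shares after early termination are not given. The size of any bias depends wholly on a regional difference that the documents do not report: 0 to 0.25 NRS points over the assumed range, and possibly zero. BAY 1817080 versus placebo and the primary MCP-Mod test are unaffected, because those four arms share one ratio in every region.

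**What to change.** For any statement that compares with elagolix:
1. Repeat the EAPP and PRO tables of SAP 6.2.3 and the key safety tables of SAP 6.4, limited in all arms to women randomised outside Japan and China.
2. In SAP 6.4.1.1, state whether elagolix is in the taste-AE model. If it is, restrict its contrasts in the same way or add region.
3. Add region and type of diagnosis by arm to the baseline table in SAP 6.1.2.
4. Keep the pooled tables for BAY versus placebo, and leave the SAP 6.2.2 MMRM as it is.

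Three clarifications would help. Reconcile the FAS definitions in the protocol and SAP. Reconcile the two statements in SAP 5.1 on the set for other endpoints. Name the SAP 6.2.2 MMRM as the source of the observed elagolix effect used as a threshold in SAP 6.2.1.1, Step 3.

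**Cost.** No new data: a region filter on selected tables, two baseline rows, and at most one model term. Elagolix contrasts would use 63 instead of 84 women per blinded arm. At SD 2.5 the SE rises from 0.386 to 2.5 × √(1/63 + 1/84) = 0.417, or 8%. At the 50/70 evaluable rate (45 and 60 women) it rises from 0.456 to 0.493, also 8%. The report should still note the open-label use of elagolix and its lack of extra liver visits, which restriction does not address.

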6.2.3.1 Endpoints on the worst EAPP

Absolute change in mean worst EAPP from baseline to the first 4 weeks/8 weeks of intervention/end of intervention (measured daily on the NRS by item 1 of the ESD)

Absolute change in mean worst EAPP from end of intervention to non-overlapping, consecutive 28-day intervals during follow-up (measured daily on the NRS by item 1 of the ESD)

Absolute change in mean worst EAPP on bleeding days from baseline to the first 4 weeks/8 weeks of intervention/end of intervention (measured on the NRS by item 1 and item 4 of the ESD)

Absolute change in mean worst EAPP on bleeding days from end of intervention to non-overlapping, consecutive 28-day intervals during follow-up (measured on the NRS by item 1 and item 4 of the ESD)

Absolute change in mean worst EAPP on non-bleeding days from baseline to the first 4 weeks/8 weeks of intervention/end of intervention (measured on the NRS by item 1 and item 4 of the ESD)

Absolute change in mean worst EAPP on non-bleeding days from end of intervention to non-overlapping, consecutive 28-day intervals during follow-up (measured on the NRS by item 1 and item 4 of the ESD)

6.2.3.2 Rescue medication

The overall amount of rescue medication during the days considered for pain evaluation will be summarized by treatment group and by 28-day time window.

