6.8.1 Standardized Rescue Pain Medication

Participants will be instructed to use standardized rescue medication only when relief of pelvic pain currently being experienced is required, i.e. not prophylactically.

Standardized rescue pain medication for endometriosis-associated pain will be prescribed for participants by the investigator and limited to ibuprofen tablets (containing 200mg or 400 mg ibuprofen per tablet, depending on local country regulations). In addition to ibuprofen, alternatively acetaminophen/paracetamol 500 mg and/or Tramadol 50 mg *may* be prescribed to participants who do not obtain sufficient relief from the study intervention and ibuprofen.

The standardized rescue medication is considered an authorized auxiliary medicinal product (not an investigational medicinal product). The maximal single and daily dose and dosing interval should be approved by the investigator and be in line with the product prescribing information for that particular dosage form in that country.

Investigators will prescribe these standardized rescue pain medications for participants at the time of entry into the screening phase, taking into consideration their preference and/or historical use of analgesics. The same rescue pain medication (type and dose preparation) used during the screening phase should be used as needed for rescue during the entire study. Participants will be instructed to contact the site if an escalation (in dose, frequency or category) in their analgesic medication from what was last prescribed by the investigator is needed, so that appropriate adjustments can be made. Participants will be instructed not to increase their total daily dose or frequency of rescue pain medication or to escalate the category of analgesic used (i.e., from ibuprofen or acetaminophen to a narcotic containing medication) unless it is necessary, after a discussion between the participant and the investigator.

Daily use of standardized rescue pain medication will be recorded by the participant in the hand-held device during the entire study. This will include specific dosing information of the permitted rescue pain medication, including dose and total number of pills/tablets within a 24-hour period and the information whether it was taken for pain in the target area or not. Local pharmacy or sites have responsibility for documentation e.g., in case of recall according to their local requirements.

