4.3.2 Diary data

28-day mean of ESD single items on pain

According to the ESD manual, the 28-day mean of an item asking for pain can be derived if at least 15 non-missing entries² are available (i. e., the number of missing entries is < 50 %).

For calculating the primary efficacy variable only, missing entries on days during a severe COVID-19 infection as recorded on the adverse event (AE) case report form (CRF) (this means in particular that the severity is not missing) will be imputed as described in Section 6.2.1 first. Thus, the 28-day will be derived only if the number of observed and imputed daily values add up to 15 or more.

Vaginal bleeding intensity

Missing bleeding diary data will be imputed following the sponsor's instruction on the evaluation of bleeding data.

4-week mean of Endometriosis Impact Scale (EIS) single items

A 4-week average score for a respondent will only be calculated if there are at least 2 not necessarily consecutive weeks of non-missing PRO data. This is consistent with the

² By design of the eDiary (ESD and EIS), if one item is missing, all items are missing. The respondents have to select an answer for an item in order to move on to the next item.

requirement of (at least) 50 % of the data to be available for calculating the 28-day mean of the ESD single items on pain.

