Ibuprofen rescue medication will be reported as 400mg. For the country in which this is collected as 200mg (Japan and USA), the number of tablets collected will be divided by 2.

Repeated measurements at the same visit

If more than one measurement flagged as valid for analysis is available for a given visit, the valid measurement closest to the start of treatment will be used in the data summaries. This is the last valid measurement before and the first valid measurement after the start of treatment visit. In the data listings, all observations will be presented.

Data Rules for laboratory measurements

For lab values reported as “<x”, “<x.x”, “<x.xx” or etc. the value for analysis used will be derived by “x/2”, “x.x/2”, “x.xx/2” etc. For lab values reported as “>x”, “>x.x”, “>x.xx” or etc. the value for analysis used will be derived by increasing the last digit by 1.

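### Rescue medication is summarised as an undivided total per 28-day window, so differences in diary completeness can pass for differences in rescue use

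*SAP*

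**What the plan says.** SAP 6.2.3.2 is a single sentence: "The overall amount of rescue medication during the days considered for pain evaluation will be summarized by treatment group and by 28-day time window". It names no divisor, unit, minimum number of days, split by drug or split by reason for use. Under SAP 6.2.3 the summary is descriptive and based on the full analysis set.

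For pain, SAP 4.3.2 says that "the 28-day mean of an item asking for pain can be derived if at least 15 non-missing entries" are available, and explains this as "the number of missing entries is < 50" per cent. A footnote there describes the eDiary design: "if one item is missing, all items are missing". Protocol 8.1.1.1 places use of rescue and other pain medication in items 9 to 11 of the same diary (the ESD), with the number of each drug recorded.

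Protocol 6.8.1 also has the diary collect "the information whether it was taken for pain in the target area or not". Besides ibuprofen, it permits "alternatively acetaminophen/paracetamol 500 mg and/or Tramadol 50 mg". The only unit rule is in SAP 4.5: "Ibuprofen rescue medication will be reported as 400mg", with tablet counts halved where the 200 mg tablet is used.

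SAP 6.2.1 handles any change in rescue intake, for EAPP or for other reasons, by the treatment policy strategy.

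**The concern.** Pain and rescue come from the same diary days but are put on different scales. Pain is a mean over the days with an entry, so a missed day drops out of numerator and denominator together. Rescue, as worded, is a total: a missed day adds nothing, exactly as if no tablet had been taken. A woman who fills in the diary less often appears to need less rescue, and so does an arm with poorer diary completion.

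This matters because of the role the table has to play. Under treatment policy, the pain comparison includes whatever rescue was taken, so a reader needs a sound description of rescue to judge whether a pain difference was helped or hidden by analgesics. Protocol section 3 accepts that a changed need for rescue can signal failure or success that worst EAPP does not fully reflect, and it foresaw supplementary analyses using a composite strategy. The current SAP describes no such analysis. The medication tables in SAP 6.1.4 count users, not amounts. That leaves 6.2.3.2 as the only planned summary of intake.

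**Working it through.** **Inputs.** Window length 28 days and minimum of 15 entries (SAP 4.3.2); rescue items missing whenever the pain item is missing (same section, footnote); total per window (SAP 6.2.3.2, read as a sum).

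**The plan's own threshold.** With 15 entries the missing share is (28 − 15)/28 = 46.4%, which is below 50%. With 14 entries it is (28 − 14)/28 = 50.0%, which is not. So 15 is the correct minimum under the stated rule.

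**Effect on a total.** Let r be true daily use, the same on observed and missed days, and n the number of entries. The recorded total is r × n; the total in a full window is r × 28. The apparent reduction is 1 − n/28, whatever r is.

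| Entries n | Total as share of a full window | Apparent reduction | Total at r = 1 unit/day | Total / n |
|---|---|---|---|---|
| 28 | 100% | 0% | 28 | 1.0 |
| 26 | 92.9% | 7.1% | 26 | 1.0 |
| 24 | 85.7% | 14.3% | 24 | 1.0 |
| 15 | 53.6% | 46.4% | 15 | 1.0 |

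Conversely, a woman going from 28 to 15 entries could raise her true daily use by a factor of 28/15 = 1.87 and still show an unchanged total. The last column shows that dividing by n removes the artefact.

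**Arm level.** If r is equal in two arms, the ratio of mean totals equals the ratio of mean entries. The documents give no completion figures, so these pairs are assumptions: means of 26 and 24 entries give a false difference of (26 − 24)/26 = 7.7%; means of 26 and 20 give (26 − 20)/26 = 23.1%.

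**If drugs were added together.** The SAP does not say that they are. Assumed switches show that the direction would depend on unit and drug:

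- In mg, ibuprofen 400 to tramadol 50: 50/400 − 1 = −87.5%.
- In mg, ibuprofen 400 to paracetamol 500: 500/400 − 1 = +25%.
- In tablets, two ibuprofen 400 mg to one tramadol: 1/2 − 1 = −50%.
- In tablets, one ibuprofen 200 mg (0.5 unit under SAP 4.5) to one tablet of another drug: 1/0.5 − 1 = +100%.

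**If reasons are added together.** Suppose EAPP use halves from 20 to 10 units while 20 units are taken for other pain (assumed figures). The total goes from 40 to 30, a fall of 25% instead of 50%.

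**How the SAP treats a comparable case.** The EIS scores in SAP 8.1.1 are summed over the four-week window and divided by the number of non-missing weeks. Rescue has no such rule.

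**The case against.** The best defence is that the consequence is small and the text less open than it looks. This is one descriptive endpoint with no test attached. The sentence confines the summary to days used for pain evaluation, which can fairly be read as windows with at least 15 entries. SAP 4.1 requires counts of available and missing data for metric variables. SAP 6.2.1 expects EAPP rescue intake to be low, and nothing in the documents suggests that diary completion will differ between arms. All of this stands as a limit on importance. It does not repair the measure: the 15-entry floor is what sets the 46% maximum, and a count of missing data printed beside a total does not correct it.

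Pooling reasons for use is also defensible. SAP 6.2.1 defines the treatment as study drug plus rescue for any reason, and an all-reasons total describes that. A split by reason is a useful addition, not the correction of an error.

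Three stronger readings are tempting, but the documents do not support them.

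- **A built-in fall from baseline.** Protocol 5.1 asks for "at least 24 daily ESD entries during the 28 consecutive days", so a reader might infer that baseline windows are fuller by rule than later ones. That requirement covers the eligibility period. SAP 4.5 takes baseline from the last 28 days before treatment, with the same 15-entry minimum as later windows.
- **A short last window after the clinical hold.** SAP 4.5 counts windows back from end of treatment and, when three full cycles are lacking, starts from the last available full cycle with at least 15 entries. On that wording a truncated cycle need not be used.
- **Drug switches show as less rescue.** Pooling across drugs is not stated; counts are recorded per drug, and the ibuprofen-only conversion fits reporting by drug at least as well. If drugs were pooled, the distortion could go either way.

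**Conclusion.** The point holds as a defect in the definition of a descriptive summary. As worded, the rescue total depends on how many diary days were completed as well as on how much was taken. Between two evaluable windows at the same daily use, the gap can reach 13/28 = 46%; smaller differences in completion give proportionately smaller gaps.

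This rests on two assumptions: that the summary is a sum, which is its natural reading, and that use on missed days resembles use on observed days. The 46% is a ceiling for an individual window. The size at arm level cannot be known from the documents and would be nil if completion were equal. The primary analysis, its significance level and the sample size are untouched. It is still worth correcting, because no other planned output describes the amount of rescue taken alongside a treatment policy estimand.

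**What to change.** In SAP 6.2.3.2, replace the total with mean rescue intake per non-missing diary day in each 28-day window: amount taken divided by number of diary entries, multiplied by 28 if a per-cycle figure is wanted. Specify also:

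- the number of diary days contributing, shown beside each figure;
- the same 15-entry minimum as for the pain mean;
- separate reporting by drug: ibuprofen in 400 mg units, paracetamol, and tramadol;
- EAPP use and other-reason use in separate rows;
- the percentage of diary days with any EAPP rescue.

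A rate per observed day still assumes that missed days resemble observed ones, but the pain mean already relies on the same assumption, so the two would be comparable.

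The cost is one paragraph of SAP text and a revised table shell. The daily entries, the number of each drug and the reason for use are already in the eDiary. The change concerns reporting only and has no bearing on how rescue medication is given.
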